- If children are involved, what is the investigator's assessment of the overall risk level for the children participating in this study? N/A
- Include an appropriate Data and Safety Monitoring Plan. Examples of DSMPs are available here <http://your.yale.edu/policies-procedures/forms/420-fr-01-data-and-safety-monitoring-plans-templates-for>
 - Minimal risk
 - Greater than minimal

Optimizing Electronic Alerts for Acute Kidney Injury
Data and Safety Monitoring Plan
420 FR.1
PI: F. [name] MSCE

The principal investigator is responsible for monitoring the data, assuring protocol compliance, and conducting the safety reviews biannually. During the review process the principal investigator will evaluate whether the study should continue unchanged, require modification/amendment, or close to enrollment. The principal investigator and the Institutional Review Board (IRB) have the authority to stop or suspend the study or require modifications.

Based on new information obtained from our recent general AKI alert study, we are taking necessary precautions to maximize patient safety in this trial. While we still feel that this is a minimal risk trial, we plan to have a Data Safety Monitoring Board review our results at an interim analysesat 50% enrollment across our four teaching hospitals. Any signal of harm will suspend the study to further enrollment.

This protocol presents minimal risks to the subjects and Unanticipated Problems Involving Risks to Subjects or Others (UPIRSOs), including adverse events, are not anticipated. In the unlikely event that such events occur, Reportable Events (which are events that are serious or life-threatening and unanticipated (or anticipated but occurring with a greater frequency than expected) and possibly, probably, or definitely related) or Unanticipated Problems Involving Risks to Subjects or Others that may require a temporary or permanent interruption of study activities will be reported immediately (if possible), followed by a written report within 5 calendar days of the Principal Investigator becoming aware of the event to the IRB (using the appropriate forms from the website) and any appropriate funding and regulatory agencies. The investigator will apprise fellow investigators and study personnel of all UPIRSOs and adverse events that occur during the conduct of this research project through regular study meetings and via email as they are reviewed by the principal investigator. The protocol's research monitor(s), e.g., DSMBs, study sponsors, funding and regulatory agencies, and regulatory and decision-making bodies will be informed of all adverse events within 5 days of the event becoming known to the principal investigator.

- d. For multi-site studies for which the Yale PI serves as the lead investigator:
 - i. How will adverse events and unanticipated problems involving risks to subjects or others be reported, reviewed and managed? All adverse events and unanticipated problems will be handled based on the protocols in place by each institution's IRB.
 - ii. What provisions are in place for management of interim results? Interim results will be managed by study personnel at Yale.
 - iii. What will the multi-site process be for protocol modifications? Any protocol modifications will be submitted to each institution's IRB for the appropriate approvals.

13. **Statistical Considerations:** Describe the statistical analyses that support the study design.

A group sequential design with Hwang-Shih-DeCanli spending functions with gamma = -4 for the efficacy boundary and gamma = -2 for the futility boundary with two interim analyses will be utilized and a two-sided Cochran-Mantel-Haenszel (CMH) method will be used for the sample size calculation to account for the four hospitals. Our preliminary data suggests that 18.2% of patients would experience the primary outcome of progression of AKI, dialysis, or mortality. We determined that a relative 20% reduction to 14.6% would be clinically significant. A total sample size of 4600 patients (i.e., 2301 per group) achieves at least 90% power to detect this degree of change. The alpha significance level of the test was set at 0.05. We will increase this

number by 10% to account for potential contamination of the effect across study arms, leading to a final sample size of 5060 individuals with a breakdown as follows based on relative numbers of beds in each hospital:

Yale New Haven Hospital: 2447

St. Raphael's Campus: 1214

Bridgeport Hospital: 910

Greenwich Hospital: 489

We will compare the rates of the primary outcomes between the intervention arm and the control arm using the chi-square test with Cochran-Mantel-Haenszel correction for the 4 study strata based on the hospital.. We will also perform exploratory analyses examining patients within the three medication categories to assess whether discontinuation rates differ by medication and, importantly, what clinical impact is apparent from alerting for those particular agents. Finally, should alerting show a clinical benefit, we will perform a mediation analysis to determine what fraction of that benefit (if any) can be attributed to medication cessation.

In addition, a retrospective examination will be performed to assess improvement in the control group before / after intervention as a measurement of contamination. We expect that providers who receive AKI alerts on some patients may be more likely to look for AKI in other patients, potentially diluting the effect of the intervention – this pre/post intervention analysis will help in assessing that level of contamination.

Because we are enrolling patients across four sites, we will do an exploratory analysis to determine the efficacy of alerts independently at each hospital.

We have specified several subgroups in whom the benefit of an AKI alert may differ from the general population. These groups will be analyzed as secondary and exploratory analyses. They include:

- Patients with AKI exposed to each of the 3 nephrotoxin categories (effects analyzed separately)
- Surgical patients (defined by admission to a surgical team)
- Subjects with baseline creatinine <1.0mg/dl
- Subjects with baseline creatinine <0.5 mg/dl
- Females (due to lower rate of increase in creatinine after AKI)
- African Americans (due to higher rate of increase in creatinine after AKI)
- Elderly subjects (age > 65, age > 70, and age > 75)
- Subjects in an ICU at the time of the alert
- Subjects who enter the study based on a 50% increase in creatinine vs. a 0.3mg/dl increase in creatinine vs. both

Finally, as the academic year progresses, new clinicians (such as residents and interns) may become more facile in their ability to recognize AKI, which may attenuate the effect of this intervention. We will model this in exploratory analyses using an intervention-by-time of year interaction term in models of the primary outcome.

Interim Analysis:

As discussed above, we plan an interim analysis, and guidelines will be given to the DSMB for stopping the trial will be for efficacy, harm, and futility. Our interim analyses will be conducted as follows:

This interim analysis will be performed at 50% enrollment at the four teaching hospitals and the trial will stop for either efficacy or futility if the p-value is $\leq .0042$ or $\geq .8952$. The p-value threshold for the final analysis of the primary outcome is set at .0498.

SECTION II: RESEARCH INVOLVING DRUGS, BIOLOGICS, RADIOTRACERS, PLACEBOS AND DEVICES

If this section (or one of its parts, A or B) is not applicable, check off N/A and delete the rest of the section.

A. RADIOTRACERS N/A

B. DRUGS/BIOLOGICS N/A

B. DEVICES N/A

SECTION III: RECRUITMENT/CONSENT AND ASSENT PROCEDURES

1. Targeted Enrollment: Give the number of subjects:

- Targeted for enrollment at Yale for this protocol: 1915 patients and approximately 2500 clinicians
- If this is a multi-site study, give the total number of subjects targeted across all sites: 4592 patients and approximately 3500 clinicians

2. Indicate recruitment methods below. Attach copies of any recruitment materials that will be used.

 Flyers	 Internet/web postings	 Radio
 Posters	 Mass email solicitation	 Telephone
 Letter	 Departmental/Center website	 Television
 Medical record review*	 Departmental/Center research boards	 Newspaper
 Departmental/Center newsletters	 Web-based clinical trial registries	 Clinicaltrails.gov
 YCCI Recruitment database	 Social Media (Twitter/Facebook):	
 Other:		

* Requests for medical records should be made through JDAT as described at

<http://medicine.yale.edu/ycci/oncore/availableservices/datarequests/datarequests.aspx>

3. Recruitment Procedures:

- Describe how potential subjects will be identified. Subjects (patients) will be identified using an electronic algorithm that interfaces with Epic databases.
- Describe how potential subjects are contacted. There will be no formal contact between patient study subjects and study personnel. We will be requesting a waiver of informed consent for patients. To educate providers of the study, we will hold pre-trial informational sessions at divisional conferences and meetings in which we will explain the purpose of the study and what to expect. We will provide an informational sheet with all relevant information and our contact information. We will also make periodic visits to the hospital floors to reeducate and answer any questions.
- Who is recruiting potential subjects? There will be no formal recruitment activities. Rather, patient subjects will be identified and enrolled into the study via an electronic algorithm embedded in Epic. All providers will be potentially exposed to the alerts and the P.I. and research coordinator of the study will educate providers as explained above.

4. Assessment of Current Health Provider Relationship for HIPAA Consideration:

Does the Investigator or any member of the research team have a direct existing clinical relationship with any potential subject?

Yes, all subjects

Yes, some of the subjects

No

If yes, describe the nature of this relationship. N/A

5. **Request for waiver of HIPAA authorization:** (When requesting a waiver of HIPAA Authorization for either the entire study, or for recruitment purposes only. Note: if you are collecting PHI as part of a phone or email screen, you must request a HIPAA waiver for recruitment purposes.)

Choose one:

For entire study

For recruitment/screening purposes only

For inclusion of non-English speaking subject if short form is being used and there is no translated HIPAA research authorization form available on the University's HIPAA website at hipaa.yale.edu.

- i. Describe why it would be impracticable to obtain the subject's authorization for use/disclosure of this data: Due to the nature of the study in that we are assessing the influence of an alert system on provider behaviors surrounding AKI, it is not feasible to consent subjects as it would severely contaminate the exposure of interest. Patients randomized to the control arm would need to be told not to inform their provider of their participation in the trial, which would severely compromise the therapeutic relationship. The only way to avoid this would be to obtain informed consent from every patient on admission to the hospital, but given that the incidence of AKI is approximately 15% of admissions, this would be impractical and would be unnecessary for the vast majority of patients. Furthermore, it would expose the roughly 85% of patients who would never be deemed eligible for the trial to the risks of loss of confidentiality present in all research with human subjects. Given that the research proposed presents no more than minimal risk to the subjects, and that no procedures are being performed that require consent outside of the research paradigm, we request a HIPAA waiver from the Institutional Review Board.
- ii. If requesting a waiver of **signed** authorization, describe why it would be impracticable to obtain the subject's signed authorization for use/disclosure of this data: *Write here*

The investigator assures that the protected health information for which a Waiver of Authorization has been requested will not be reused or disclosed to any person or entity other than those listed in this application, except as required by law, for authorized oversight of this research study, or as specifically approved for use in another study by an IRB.

Researchers are reminded that unauthorized disclosures of PHI to individuals outside of the Yale HIPAA-Covered entity must be accounted for in the "accounting for disclosures log", by subject name, purpose, date, recipients, and a description of information provided. Logs are to be forwarded to the Deputy HIPAA Privacy Officer.

6. **Process of Consent/Accent:** Describe the setting and conditions under which consent/assent will be obtained, including parental permission or surrogate permission and the steps taken to ensure subjects' independent decision-making.
Applicable to clinician subjects – we will perform outreach through short presentations at divisional conferences and meetings and through regular visits to hospital floors to engage directly with providers. A study Information Sheet will also be handed out to clinicians.

7. **Evaluation of Subject(s) Capacity to Provide Informed Consent/Accent:** Indicate how the personnel obtaining consent will assess the potential subject's ability and capacity to consent to the research being proposed.

N/A

8. **Non-English Speaking Subjects:** Explain provisions in place to ensure comprehension for research involving non-English speaking subjects. If enrollment of these subjects is anticipated, translated copies of all consent materials must be submitted for approval prior to use.

N/A

As a limited alternative to the above requirement, will you use the short form* for consenting process if you unexpectedly encounter a non-English speaking individual interested in study participation and the translation of the long form is not possible prior to intended enrollment? YES NO

Note* If more than 2 study participants are enrolled using a short form translated into the same language, then the full consent form should be translated into that language for use the next time a subject speaking that language is to be enrolled.

Several translated short form templates are available on the HRPP website (yale.edu/hrpp) and translated HIPAA Research Authorization Forms are available on the HIPAA website (hipaa.yale.edu). If the translation of the short form is not available on our website, then the translated short form needs to be submitted to the IRB office for approval via modification prior to enrolling the subject. *Please review the guidance and presentation on use of the short form available on the HRPP website.*

If using a short form without a translated HIPAA Research Authorization Form, please request a HIPAA waiver in the section above.

9. **Consent Waiver:** In certain circumstances, the HIC may grant a waiver of signed consent, or a full waiver of consent, depending on the study. If you will request either a waiver of consent, or a waiver of signed consent for this study, complete the appropriate section below.

Not Requesting any consent waivers

Requesting a waiver of signed consent:

Recruitment/Screening only (if for recruitment, the questions in the box below will apply to recruitment activities only)
 Entire Study (Note that an information sheet may be required.) For clinician subjects.

For a waiver of signed consent, address the following:

- Would the signed consent form be the only record linking the subject and the research? YES NO
- Does a breach of confidentiality constitute the principal risk to subjects? YES NO

OR

- Does the research pose greater than minimal risk? YES NO
- Does the research include any activities that would require signed consent in a non-research context? YES NO

Requesting a waiver of consent:

Recruitment/Screening only (if for recruitment, the questions in the box below will apply to recruitment activities only)
 Entire Study - for patient subjects

For a full waiver of consent, please address all of the following:

- Does the research pose greater than minimal risk to subjects?
 Yes *If you answered yes, stop. A waiver cannot be granted.*
 No
- Will the waiver adversely affect subjects' rights and welfare? YES NO
- Why would the research be impracticable to conduct without the waiver? Due to the nature of the study, it is not feasible to consent subjects, as it would severely contaminate the exposure of interest. Patients randomized to the control arm would need to be told not to inform their provider of their participation in the trial, which would severely compromise the therapeutic relationship. The only way to avoid this would be to obtain informed consent from every patient on admission to the hospital, but given that the incidence of AKI is approximately 15% of admissions, this would be impractical and would be unnecessary for the vast majority of patients. Given that the research proposed presents no more than minimal risk to the subjects, and that no procedures are being performed that require consent outside of the research paradigm, we will request a waiver of consent from the Institutional Review Board.
- Where appropriate, how will pertinent information be returned to, or shared with subjects at a later date? The results of this study will not be pertinent to the subjects, as the effect of the alert is expected to be transient and should have no impact on their future quality of life beyond that measured by the outcome of the study itself. Moreover, post-hoc disclosure of the nature of the study to the subjects may generate undue stress and concern on the part of the subject as to the quality of their overall clinical care. As most patients are not familiar with AKI, informing them to the presence of the disease without offering a tangible benefit may further increase anxiety surrounding their overall health. We will update all clinicians of the results of this trial after trial completion. We are not collecting data that would tie a specific clinician to an outcome. For example, while we would inform clinicians that the alerts decreased the use of certain drugs, we will not be able to tell them what their specific rate of drug continuation or discontinuation would be.

SECTION IV: PROTECTION OF RESEARCH SUBJECTS

Confidentiality & Security of Data:

1. What protected health information (medical information along with the HIPAA identifiers) about subjects will be collected and used for the research? Patient Name, SSN, zip code, DOB, Admission/discharge dates, medical record number, laboratory values, provider notes, medical procedures, medical history, medication lists, imaging results.
2. How will the research data be collected, recorded and stored? All data, both patient and provider, will be collected electronically by an automated algorithm that interfaces with the EPIC user database system, developed by JDAT. Data will be skimmed from the EHR, processed electronically, encrypted, deidentified, and transferred to a secure server for storage and later analysis. As discussed above, the primary dataset will contain no PHI. We will maintain a separate “linking file” that contains all PHI and will be stored on a separate server to limit the risk of accidental disclosure. The linking file is being maintained for potential future linking to national databases of death and dialysis.

3. How will the digital data be stored? CD DVD Flash Drive Portable Hard Drive Secured Server Laptop Computer Desktop Computer Other
4. What methods and procedures will be used to safeguard the confidentiality and security of the identifiable study data and the storage media indicated above during and after the subject's participation in the study? All data will be stored on an encrypted, HIPAA-Compliant server with 2-factor authentication. Data will not be stored on personal computing devices of any kind. The server will only be accessible from within the Yale firewall or via VPN. No portable devices will be used to store study data at any time.

All portable devices must contain encryption software, per University Policy 5100. If there is a technical reason a device cannot be encrypted please submit an exception request to the Information Security, Policy and Compliance Office by clicking on url <http://its.yale.edu/egrc> or email [contact]

5. What will be done with the data when the research is completed? Are there plans to destroy the identifiable data? If yes, describe how, by whom and when identifiers will be destroyed. If no, describe how the data and/or identifiers will be secured. PHI will be deleted by study personnel within one year of closing of the study.
6. If appropriate, has a Certificate of Confidentiality been obtained? A Certificate of Confidentiality automatically covers this NIH-funded research.

SECTION V: POTENTIAL BENEFITS

Potential Benefits: Identify any benefits that may be reasonably expected to result from the research, either to the subject(s) or to society at large. (Payment of subjects is not considered a benefit in this context of the risk benefit assessment.)

Patient-Subjects in this study may benefit from their provider being given information about the presence of acute kidney injury concurrent with the usage of nephrotoxic agents. This benefit may be derived from closer monitoring of physiologic status, cessation of the nephrotoxic agents, diagnostic interventions, or other factors. Regardless of the outcome for participants, the results of these studies may lead to significant societal benefit, as positive results would lead to broader adoption of an effective alerting system that would lead to improved treatment for AKI patients, and a negative study would lead to less enthusiastic adoption of ineffective alerting that would otherwise contribute to alert fatigue.

SECTION VI: RESEARCH ALTERNATIVES AND ECONOMIC CONSIDERATIONS

1. **Alternatives:** What other alternatives are available to the study subjects outside of the research?
Usual hospital care
2. **Payments for Participation (Economic Considerations):** Describe any payments that will be made to subjects, the amount and schedule of payments, and the conditions for receiving this compensation.
N/A
3. **Costs for Participation (Economic Considerations):** Clearly describe the subject's costs associated with participation in the research, and the interventions or procedures of the study that will be provided at no cost to subjects.
N/A
4. **In Case of Injury:** This section is required for any research involving more than minimal risk, and for minimal risk research that presents the potential for physical harm (e.g., research involving blood draws).
N/A

- a. Will medical treatment be available if research-related injury occurs? *Write here*
- b. Where and from whom may treatment be obtained? *Write here*
- c. Are there any limits to the treatment being provided? *Write here*
- d. Who will pay for this treatment? *Write here*
- e. How will the medical treatment be accessed by subjects? *Write here*

IMPORTANT REMINDERS

Will this study have a billable service? Yes No

A billable service is defined as any service rendered to a study subject that, if he/she was not on a study, would normally generate a bill from either Yale-New Haven Hospital or Yale Medical Group to the patient or the patient's insurer. The service may or may not be performed by the research staff on your study, but may be provided by professionals within either Yale-New Haven Hospital or Yale Medical Group (examples include x-rays, MRIs, CT scans, specimens sent to central labs, or specimens sent to pathology). Notes: 1. There is no distinction made whether the service is paid for by the subject or their insurance (Standard of Care) or by the study's funding mechanism (Research Sponsored). 2. This generally includes new services or orders placed in EPIC for research subjects.

If answered, "yes", this study will need to be set up in OnCore, Yale's clinical research management system, for Epic to appropriately route research related charges. Please contact [contact]

Are there any procedures involved in this protocol that will be performed at YNHH or one of its affiliated entities?
Yes No

If Yes, please answer questions a through c and note instructions below.

- a. Does your YNHH privilege delineation currently include the **specific procedure** that you will perform? Yes No

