Identification of subjects with AKI will be performed entirely within the Epic medical records system based on inclusion and exclusion criteria outlined below. This will be done using a best-practice alert build developed by the JDAT team at Yale. It works by examining the most recent creatinine value and comparing it to the minimum value in the past 48 hours or the past 7 days. If the current value is 0.3 mg/dl above the 48-hour minimum, or 50% higher than the 7 day minimum, the patient will be defined as having AKI. If, in addition, the patient has an active order for one of our targeted nephrotoxic agents, he or she will be automatically enrolled. Enrolled patients will automatically and immediately be randomized either into the intervention group or the usual care group. Randomization will be done within Epic via a simple randomization method using concealed allocation via a random number rule that is incorporated in the alert. This ensures that, upon meeting criteria, each patient is immediately and randomly assigned to an arm. Logic checks within the alerts ensure that once a patient is assigned to an arm, they remain on that arm for the remainder of their hospital stay.

Study Intervention:

Patients in the intervention (alert) group will have an alert generated within the electronic medical record system. This will consist of a “pop-up” within Epic when a provider accesses the patient’s record and opens the order entry screen such that it appears at the most relevant place in a provider’s workflow. This alert notifies the physician that the patient has AKI and has recently been given at least one dose of a nephrotoxic medication(s). It also explains that this alert does not fire for all patients and that the patient is part of a randomized trial. A link to our study website is provided. The alert outlines each targeted medication that

the patient is on, and links to the medication entry system. An example of what this alert will look like is as follows:

Medication Alerts (1)

① AKI Alert - Consider Clinical Indication for the Following Medications!

Most recent creatinine: 1.5 mg/dl
Lowest creatinine in past 7 days: 0.62 mg/dl
Highest creatinine in past 7 days: 1.51 mg/dl

ACEI/ARB/RAAS - These medications decrease pressure in the glomerulus, decreasing GFR. If you stop this agent, please consider an alternative anti-hypertensive agent and closely monitor blood pressure. (1h ago, onward)

Medication	Route	Frequency	Start Date	End Date

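### The primary test adjusts for hospital only; prespecified adjustment for baseline variables already within reach is an optional, low-cost gain in precision

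*Combined protocol and SAP*

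**What the plan says.** Section I, item 13 (Statistical Considerations) compares the primary outcome between arms with a "chi-square test with Cochran-Mantel-Haenszel correction for the 4 study strata based on the hospital". Sizing uses the same approach: a "two-sided Cochran-Mantel-Haenszel (CMH) method will be used for the sample size calculation to account for the four hospitals". On error rates it says "The alpha significance level of the test was set at 0.05", and the Interim Analysis paragraph adds "The p-value threshold for the final analysis of the primary outcome is set at .0498". No adjusted primary, secondary or sensitivity analysis is named.

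Patient-level baseline variables appear elsewhere in the plan:

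- The subgroup list in item 13 includes surgical team, baseline creatinine, sex, age, entry criterion, drug class and "Subjects in an ICU at the time of the alert".
- Section I, item 4 (Subject Eligibility and Randomization) has the alert work by "examining the most recent creatinine value and comparing it to the minimum value in the past 48 hours or the past 7 days", so both values exist when the arm is assigned.
- Section IV, item 1 lists "laboratory values, provider notes, medical procedures, medical history, medication lists, imaging results" among the data to be collected and used, and item 2 says collection is automated.

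The only regression of the primary outcome is exploratory, "using an intervention-by-time of year interaction term in models of the primary outcome". It names no baseline covariates.

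**The concern.** In a randomised trial with a binary outcome, adjusting for baseline variables that predict the outcome reduces the variance of the treatment comparison without biasing it. The planned test takes that benefit from hospital alone. Creatinine at randomisation, ICU status and age plausibly predict progression, dialysis or death better than hospital does.

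Nothing here threatens validity. What could be lost is power, and the plan gives a reason to want a reserve: item 13 expects contamination of the control arm to dilute the effect. Adjustment would provide some reserve with no added enrolment or data collection.

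**Working it through.** **1. Reproduce the plan's sample size.** Inputs from item 13: 18.2% versus 14.6%, two-sided 0.05, 90% power, spending parameters −4 (efficacy) and −2 (futility). With mean rate 0.164, the fixed-design size per arm is

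[1.960·√(2·0.164·0.836) + 1.282·√(0.182·0.818 + 0.146·0.854)]² / 0.036² = 2222, or 4444 in total.

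One look at 50% inflates this by 1.0305 (binding futility) or 1.0429 (non-binding), giving 4579 or 4635. The plan's 4600 lies between them, and 4600 × 1.10 = 5060. In 200,000 simulated trials of 4600 with hospitals in the planned proportions, the CMH test had type I error 0.0505 and power 0.911. The planned test is valid and meets its stated power.

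**2. What hospital alone contributes.** The outcome tables in Section I, item 11, both arms pooled, give YNH 201/911 (22.1%), SRC 82/575 (14.3%), BH 70/401 (17.5%) and GH 41/273 (15.0%). Hospital alone has a c-statistic of 0.56 and explains about 0.8% of outcome variance.

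For rates p0 = 0.182 and p1 = 0.1456 (exactly 20% lower), N × Var of the risk difference is:

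- Unstratified: 2·0.182·0.818 + 2·0.1456·0.8544 = 0.5466.
- Stratified by hospital (rates above scaled to 18.2% and 14.56%, planned shares 2447/1214/910/489): 0.5429.

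The ratio is 0.993, worth about 35 to 40 patients. CMH already has this.

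**3. What further covariates could add.** Let logit P(event) = α(arm) + σ·score, with a standard normal score and α set so that the marginal rates stay at 18.2% and 14.56%. With m0 and m1 the individual risks under each arm,

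N × Var = 2E[m0(1−m0)] + 2E[m1(1−m1)] + Var(m1−m0).

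For c = 0.70 (σ = 0.774): 2(0.1367) + 2(0.1155) + 0.0003 = 0.5046 before rounding of the terms. The ratio to the stratified value is 0.5046/0.5429 = 0.929. An unadjusted trial would need 5060 × (0.5429/0.5046 − 1) = 384 more patients for the same precision.

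**4. Power at 5060.** This uses the plan's thresholds (0.0042 at 50%, 0.0498 at the end), one interim look and no futility stop. For CMH, z = 0.0364/√(0.5429/5060) = 3.51. The final look alone gives Φ(3.51 − 1.96) ≈ 94.0%, and the interim look adds less than 0.1 point. The diluted case multiplies the risk difference by 0.9: 0.9 × 0.0364 = 0.0328.

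| Assumed c (hospital included) | σ | Variance ratio to CMH | Extra patients CMH would need | Power | Power, effect 10% smaller |
|---|---|---|---|---|---|
| CMH as planned | – | 1 | – | 94.0% | 88.3% |
| 0.60 | 0.362 | 0.989 | 57 | 94.3% | 88.7% |
| 0.65 | 0.557 | 0.965 | 182 | 94.7% | 89.4% |
| 0.70 | 0.774 | 0.929 | 384 | 95.4% | 90.5% |
| 0.75 | 1.025 | 0.880 | 692 | 96.3% | 91.9% |

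**5. Cross-check by another route.** In simulated trials of 4600 (1,200 per scenario), adjusted logistic regression raised power from 0.91–0.92 to 0.93–0.94. Its type I error was 0.043 to 0.065, with a Monte Carlo standard error of about 0.006.

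**The case against.** The strongest reply is that nothing is broken. Sizing and test agree, type I error is correct, and the stated power is met. This is accepted, and it is why the point is optional.

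Second, the gain rests on an assumed c-statistic. The only observed anchor is hospital at 0.56, which CMH already uses. This stands: the table shows what could be gained, not what is expected.

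Third, the smallest gains are no larger than a rounding choice. Using the printed 14.6% instead of 14.56% lowers baseline power from 94.0% to 93.5%. That is true of the level, but the differences between rows stay about the same.

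Fourth, the plan already adds 10% to enrolment for contamination and plans a pre/post contamination analysis. But offsetting an effect 10% smaller takes 1/0.9² = 1.23 times the patients, not 1.10, so power in that case falls to 88.3%. The plan does not state a degree of dilution; 10% is an assumption.

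Fifth, complete covariates are inferred. Section IV, item 1 is a confidentiality item, not a baseline dataset, and ICU status and surgical team appear only as subgroup labels. This stands, and it is why a missing-covariate rule is needed.

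Sixth, item 13 announces two interim analyses while its Interim Analysis paragraph describes one. That needs reconciling but affects CMH and an adjusted test alike.

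**Conclusion.** The point holds as an optional improvement. The hospital-stratified CMH test is valid, and leaving out other covariates is a missed efficiency option, not an error. For an assumed c-statistic of 0.60 to 0.75, adjustment cuts the variance by about 1% to 12% beyond CMH. That adds 0.3 to 2.3 percentage points of power at the planned effect and 0.4 to 3.6 points if the effect is 10% smaller. In the diluted case, power regains 90% at a c of about 0.70. If the full model predicts no better than hospital, the gain is nil.

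**What to change.** Before unblinding, either record that adjustment was considered and CMH kept, or prespecify the following as the primary analysis:

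- A standardised (g-computation) risk difference and risk ratio from one logistic model, with robust variance.
- Terms for arm, hospital and a short fixed list measured at or before randomisation: age, sex, medical or surgical status, creatinine and AKI stage at randomisation, lowest creatinine in the prior 7 days, ICU status and drug class. The creatinine terms overlap and could be trimmed.
- A rule for missing covariates, for example arm-blind imputation with a missing indicator.
- A fallback to CMH if the model fails to converge.
- The same test at interim and final, against the plan's p-value thresholds once the number of looks is reconciled.
- The hospital-stratified CMH result as the supportive unadjusted analysis.

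A smaller step is to keep CMH as primary and add the adjusted analysis as supportive, but then the primary test gains no power.

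The cost is a few lines of SAP text, some programming at interim and final, and covariate definitions fixed in advance. Baseline creatinine is not defined at present; defining it would also serve the planned subgroups. No new data collection is foreseen, provided the variables are confirmed to be in the extract.
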